### **Statistical Analyses:**

#### ***Efficacy Analysis***

Efficacy analysis will be based on changes from baseline to Day 56 in AK lesions. Comparative analysis of the changes will be applied between each of the active groups versus the placebo group using the two-sample t-test or non-parametric Wilcoxon-Mann-Whitney rank sum test for independent samples or Median test (as is appropriate). In the event that the number of baseline lesions is different between the treatment groups, then relative changes (%) will be analyzed as well.

The overall change and the trend of differences in the changes over time between the groups will be analyzed using mixed-effect model for repeated measures. The model will include changes at any time, the fixed effect time and the interaction of treatment and time. The model will be adjusted for baseline measures and for other relevant covariates.

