#### 17.2.1 Efficacy Analysis

The efficacy analysis will be performed with the ITT, mITT, and PP populations (see Section 17.5.2). The primary efficacy endpoint is the change from baseline in number of AK lesions. If the baseline lesions number will be found different between the treatment groups, then relative change (%) will be analyzed as well. The within-group absolute changes (decrease) in AK number of lesions from baseline to each visit will be analyzed using paired t-test or signed rank test for two means (paired observations, as is appropriate).

Comparative analysis of the above changes will be applied between each of the active groups versus the placebo group using the two-sample t-test, the non-parametric Wilcoxon-Mann-Whitney rank sum test for independent samples, or the Median test (as appropriate).

If no statistically significant differences are observed between the two active VDA-1102 groups then these two groups will be pooled and compared to the placebo group in order to achieve higher statistical power.

The overall effect and trend of differences in the changes over time between the groups will be analyzed using a mixed-effect model for repeated measures. The model will include changes from baseline at any time, the fixed effect time, and the interaction of treatment and time. Contrast will be calculated for each time point (Days 7, 14, 28, 35 and 56) versus baseline and the overall effect. The model will be adjusted for baseline measure and for other covariates suspected as affecting the outcome and which will be found different between the treatment groups.

In case the baseline number of lesions differs between the groups, analysis of relative change (%) will be applied as well.

Chi-square test or Fisher's exact test (as is appropriate) will be used for analyzing the difference in percent of subjects with complete clearance of study AK lesions at the end of the treatment. Logistic regression will be applied for analyzing the difference in proportions with adjustment for baseline measure and for other covariates suspected as affecting the outcome and which will be found different between the treatment groups.

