#### 5.3.2 Sample Size Justification

5.3.2.1 The primary objective of the trial is to compare the reduction on Day 56 in the number of the AK lesions (or % reduction if baseline measure will be found different between the groups) in the Treatment Field of subjects receiving 5% or 10% VDA-1102 ointment to the reduction in the number of AK lesions in subjects receiving placebo. The sample size calculation was based on demonstrating effect size of 0.83 using a two group t-test with a 0.045 two-sided significance level. The total significance level of 5% was divided between the interim analysis 0.5% (0.005) and the final analysis 4.5% (0.045). The sample size calculation was based on the final significance. The spending function calculation for alpha will be performed using the O'Brien-Fleming approach. Assuming a drop-out rate of 10%, approximately 84 subjects will be recruited in order to complete the study with a sample of approximately 75 evaluable subjects.

5.3.2.2 A sample size of 25 in each group will have 80% power to detect an effect size of 0.83 using a two group T-test with a 0.045 two-sided significance level.

	DOCUMENT NUMBER: 029-BST-PLN-001	PAGE: 22 of 45
TITLE: Statistical Analysis Plan for study: A Phase 2 Randomized, Double-Blind, Placebo-Controlled, Parallel-Cohort Study to Evaluate the Efficacy, Safety, Tolerability, and Pharmacokinetics of Once-Daily Application of Topical VDA-1102 Ointment for 28 Days in Subjects with Actinic Keratosis	EFFECTIVE DATE : 22/MAY/2017 REVISION NUMBER : 2.0	

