5.6.5.6 The overall effect and trend of differences in the decrease over time between the groups will be analyzed using a mixed-effect model for repeated measures. The model will include decrease from baseline at any time, the fixed effect time, and the interaction of treatment and time. Contrast will be calculated for each time point (Days 7, 14, 28 and 56) versus baseline and the overall effect. The model will be adjusted for site and for other covariates suspected as affecting the outcome and which will be found different between the treatment groups.

5.6.5.7 For the ANCOVA analysis, logistic regression and mixed-effect model for repeated measures detailed above, if necessary, grouping of sites will be done based on similarities and differences observed between sites by post-hoc contrasts of ANOVA.

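### The supportive repeated-measures model lists no treatment main effect, so its treatment-by-time term tests for any difference at any visit and cannot serve as the test of trend

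*SAP*

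**What the plan says.** SAP 5.6.5.6 gives the model two jobs: "The overall effect and trend of differences in the decrease over time between the groups will be analyzed using a mixed-effect model". It then lists the terms: "The model will include decrease from baseline at any time, the fixed effect time, and the interaction of treatment and time". Protocol 17.2.1 has "The model will include changes from baseline at any time, the fixed effect time, and the interaction of treatment and time" and the protocol synopsis has "The model will include changes at any time, the fixed effect time and the interaction of treatment and time". The adjustment sentence in the SAP, "The model will be adjusted for site and for other covariates suspected as affecting the outcome", adds site and imbalanced covariates but not treatment.

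The SAP also plans contrasts: "Contrast will be calculated for each time point (Days 7, 14, 28 and 56) versus baseline and the overall effect". The protocol's list adds Day 35: "Contrast will be calculated for each time point (Days 7, 14, 28, 35 and 56) versus baseline and the overall effect".

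Neither document says whether time is categorical or continuous, which covariance structure applies, what significance level this model uses, or which test answers the trend question. The Day 56 comparison of each active arm with placebo is specified separately in SAP 5.6.5.2 (t-test, rank test or median test, and ANCOVA).

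**The concern.** In the model as listed, treatment enters only through its interaction with time. That term therefore carries the average treatment effect as well as any change in the effect across visits. An effect that is the same at every visit makes the term significant, although there is no trend.

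The other planned output does not fill the gap. The listed contrasts are each visit against baseline and the overall effect; none compares the treatment difference between visits. Someone looking for the trend result has only the interaction term to turn to. What is at stake is the statement about onset and time course, which is what this model adds to the Day 56 test. SAP 5.6.6.1 also repeats the primary comparative analyses for the count of lesions of grade 2 or higher and for the grade-weighted count, so the same specification carries over to those.

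**Working it through.** **Inputs.** Three arms, 1:1:1; 25 per arm and an effect size of 0.83 (SAP 5.3.2); visits at Days 7, 14, 28 and 56 (SAP 5.6.5.6). Assumed, because the documents do not give them: within-subject correlation, complete data, unit SD at each visit, compound-symmetric errors and a 5% test level.

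**The plan's own figure.** SAP 5.3.2 states: "A sample size of 25 in each group will have 80% power to detect an effect size of 0.83", at two-sided 0.045. The noncentrality is 0.83 × √(25/2) = 2.93 with 48 df, which gives power of 80.7%; 24 per arm gives 79.0%. For dropout, 75 / 0.9 = 83.3, rounded up to 84. The stated sample size is reproduced.

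**Degrees of freedom, categorical time.** The ranks of the fixed-effect designs with 4 visits are:
- time only: 4
- time + treatment: 6
- time + treatment × time: 12, one mean per arm and visit

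Without a main effect, treatment × time has 12 − 4 = 8 df: two active-minus-placebo differences at each of four visits, all set to zero. With the main effect it has 12 − 6 = 6 df: each of those differences equal across visits. The extra 2 df are the treatment main effect. With the protocol's five visits the counts are 15 − 5 = 10 and 15 − 7 = 8.

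**Rejection rates, categorical time, 4 visits.** Simulation with an unstructured covariance and the Pillai multivariate test, 5,000 to 6,000 trials per row, both active arms shifted equally.

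| Assumed effect at Days 7/14/28/56 (SD) | Correlation | Listed term, 8 df | Interaction with main effect in model, 6 df |
|---|---|---|---|
| 0.83 at all four | 0.5 | 84% | about 5% |
| 0.83 at all four | 0.7 | 74% | about 5% |
| 0.83 at all four | 0.8 | 69% | about 5% |
| 0.2 / 0.5 / 0.83 / 0.83 | 0.5 | 84% | 54% |
| 0.2 / 0.5 / 0.83 / 0.83 | 0.7 | 92% | 81% |
| 0 at all four | 0.5 to 0.8 | 4–5% | 4–5% |

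A separate simulation of the constant case gave 77% at correlation 0.7. At correlation 0.3 the listed term rejects in 94% under the constant 0.83 SD effect. At a constant 0.4 SD it rejects in 29%, 22% and 16% at correlations 0.3, 0.5 and 0.8.

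**What does not change.** In a simulated data set fitted both ways with categorical time, the treatment differences by visit, their standard errors and the overall contrast agreed to every printed digit. The two models span the same 12 means.

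**Continuous time.** With linear time, a common intercept and treatment-specific slopes, a constant 0.83 SD effect is forced into the slopes. The fitted difference then appears to grow by 0.65, 0.44 or 0.16 SD from Day 7 to Day 56 at correlation 0.3, 0.5 or 0.8. The slope test rejects in 82%, 52% or 17%, against 5% with the main effect in the model. On this reading the estimates are distorted as well as the test.

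**The case against.** The strongest reply is that little depends on this term. The SAP never names the interaction test as the trend test and attaches no decision rule or significance level to it. The overall effect has its own planned contrast, identical under either set of terms when time is categorical. The Day 56 primary tests do not use the model, and the Day 84 comparison in SAP 5.6.6.8 is a separate two-sample analysis. All of this stands.

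The constant-effect case is also an extreme. It puts the full 0.83 SD at Day 7. The only onset evidence in the documents is the mouse study in protocol 5.6.1, which points to early effects with full benefit after three to four weeks. A build-up of that kind is a genuine treatment-by-time interaction, and the correct test would often detect it too. This also stands, which is why the 70–84% must be read as the no-trend case only.

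A reader might go further and infer that the overall effect is untested, or that the listed term loses power for it. The documents do not support that: the overall contrast is planned, and nothing says to read the 8-df term in its place. Nor does the power comparison run one way. Under the constant effect the 2-df main effect has more power than the listed term (97% and 93% at correlations 0.5 and 0.7), but under the build-up profile above it has less (about 77% and 67%).

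Finally, the wording may be shorthand, since it omits the covariance structure too. That is possible. But the same two terms appear in all three descriptions, and SAP 5.6.1.1 treats analyses it does not mention as unplanned, so the plan should not depend on a silent correction.

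**Conclusion.** The point holds for a supportive model. As written, with categorical time, the treatment-by-time term tests any difference at any of the four visits (8 df) and cannot answer the trend question (6 df). Under a constant 0.83 SD effect, with 25 per arm, complete data and correlation 0.5 to 0.8, it would be significant in roughly 70–84% of trials, against about 5% for the correct test. The gap shrinks for smaller constant effects and for effects that build up, and with no drug effect both tests keep their level.

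It would be tempting to conclude that the trial will report a false trend or that its primary result is at risk. Neither follows. The first needs both a roughly constant effect and an analyst who reads this term as the trend; the second is excluded because the Day 56 tests are separate. If time were fitted as continuous, the model's fitted differences would be distorted too, so the choice needs to be stated.

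**What to change.** In SAP 5.6.5.6, list the fixed effects as treatment, time (categorical) and treatment × time, plus the existing adjustment terms. State that the trend is tested by treatment × time with the main effect in the model, and that the overall effect is tested by the planned overall contrast, meaning the treatment difference averaged over visits. The change carries through to the variables in SAP 5.6.6.1. It costs one phrase in the SAP and one model term, with no extra data and no change in sample size.

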## 2. PROTOCOL SYNOPSIS

Title of Study: A Phase 2 Randomized, Double-Blind, Placebo-Controlled, Parallel-Cohort Study to Evaluate the Efficacy, Safety, Tolerability, and Pharmacokinetics of Once-Daily Application of Topical VDA-1102 Ointment for 28 Days in Subjects with Actinic Keratosis	
Study Center(s): Approximately 6 sites in the US and 3 in Israel	
Study Duration: 11 months	Phases of Development: Phase 2
Study Objectives:	

Primary Objective: To compare the reduction on Day 56 in the number of the actinic keratosis (AK) lesions in the Treatment Field of subjects receiving once-daily topical 5% or 10% VDA-1102 ointment for 28 days to the reduction in the number of AK lesions in subjects receiving placebo.
	
Secondary Objectives:	

 
• To evaluate the systemic and local (skin) safety and tolerability of once-daily topical application of 5% or 10% VDA-1102 ointment or placebo for 28 days in adult subjects with AK.
 
• To assess the systemic exposure of VDA-1102 and jasmonic acid, its primary metabolite, at selected time points during topical application of 5% or 10% VDA-1102 ointment or placebo for 28 days in adult subjects with AK.
 
	
Exploratory Objectives:	

 
• To compare the proportion of subjects receiving 28 days of 5% or 10% VDA-1102 who on Day 56 had complete clearance of AK lesions to subjects receiving placebo.
 
• To compare the reduction on Day 84 in the number of the actinic keratosis (AK) lesions in the Treatment Field of subjects receiving once-daily topical 5% or 10% VDA-1102 ointment for 28 days to the reduction in the number of AK lesions in subjects receiving placebo.
 
	
Study Design:	

This Phase 2 clinical trial is a multi-center, randomized, double-blind, placebo-controlled, multiple-dose, parallel-cohort study involving the once-daily non-occluded, topical dermal application of the study drug (5% or 10% VDA-1102 ointment, or placebo) for 28 days.
	

Approximately 84 subjects will be enrolled in this study in order to obtain at least 75 evaluable subjects by the end of the trial. Fifteen (15) of these subjects will constitute a Nested Phase 1b Safety Study Sub-Cohort, and a maximum of 18 of the 84 subjects will be included in a PK Study Sub-Cohort. These 2 sub-cohorts may overlap and are described below.
	

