## 12. CONDUCT OF THE STUDY

### 12.1 Study Blinding and Randomization

#### 12.1.1 Randomization

Assignment of study drug will be performed using a web-based Interactive Responsive Technology (IRT)-based randomization system. On Day 1 Pre-Dose, after confirming the subject's eligibility, the Investigator (or his designee) may approve the subject's blinded randomization.

The web-based IRT will randomize subjects in a fashion that will maintain a balance among the 3 treatment groups (5% and 10% VDA-1102, and placebo) across all subjects enrolled (not per site) and within the PK Study Sub-Cohort.

Subjects who withdraw or are terminated after 1 study dose has been applied will not be replaced in the trial.

Should a subject lose or destroy a tube, the IRT is capable of assigning additional study drug to each subject with the appropriate treatment assignment.

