### 5.2.5 Randomization, Blinding and Un-blinding

- 5.2.5.1 Assignment of study drug will be performed using a web-based Interactive Responsive Technology (IRT)-based randomization system (TrialMaster, OmniComm Systems, Fort Lauderdale, FL USA) . On Day 1 Pre-dose Visit, after confirming the subject's eligibility, the Investigator (or his designee) may approve the subject's blinded randomization.
- 5.2.5.2 The web-based IRT will randomize subjects in a fashion that will maintain a balance among the 3 treatment groups (5% and 10% VDA-1102, and placebo) across all subjects enrolled (not per site) and within the PK Study Sub-Cohort. (For further details see "VDA-CP-03 final randomization plan v1.1 15-06-2016.docx")
- 5.2.5.3 Subjects who withdraw or are terminated after the first study dose has been applied will not be replaced in the trial. Subjects who withdraw or are terminated before the first study dose has been applied due to error or violation of an enrollement criterion will be replaced and not included in the Intent-To-Treat (ITT) population.
- 5.2.5.4 All site staff at the investigative sites, Sponsor, CROs, and vendors as well as all enrolled subjects will be masked to the study drug assignments throughout the trial. One pre-designated statistician at MediStat (Tel Aviv, Israel) will have access to the blinded treatment assignments and be responsible for all activities that require un-blinding, including the per protocol Interim Efficacy Analysis.
- 5.2.5.5 In the event of an emergency, the Investigator (or designee) should contact the Study Medical Monitor to discuss the case before un-blinding of an individual subject's treatment code is broken by the site. If the medical condition of the subject warrants immediate un-blinding, the treatment assignment of the subject may be obtained from the IWRS without first consulting the Study Medical Monitor. However, the site must contact the Study Medical Monitor as soon as possible after the un-blinding.

	DOCUMENT NUMBER: 029-BST-PLN-001	PAGE: 21 of 45
TITLE: Statistical Analysis Plan for study: A Phase 2 Randomized, Double-Blind, Placebo-Controlled, Parallel-Cohort Study to Evaluate the Efficacy, Safety, Tolerability, and Pharmacokinetics of Once-Daily Application of Topical VDA-1102 Ointment for 28 Days in Subjects with Actinic Keratosis	EFFECTIVE DATE : 22/MAY/2017 REVISION NUMBER : 2.0	

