## 5.6.5 Efficacy Primary Analysis

- 5.6.5.1 The efficacy analysis will be performed with the ITT, mITT and PP populations (see Tables 14.2-1 - 14.2-9). The primary efficacy endpoint is the decrease from baseline in number of AK lesions. The within-group decrease in number of AK lesions from baseline to each visit will be analyzed using paired t-test or signed rank test for two means (paired observations, as is appropriate).
- 5.6.5.2 Comparative analysis of the decrease at Day 56 (mentioned above) will be applied between each of the active groups versus the placebo group using the two-sample t-test, the non-parametric Wilcoxon-Mann-Whitney rank sum test for independent samples, or the Median test (as appropriate) and using the Analysis of Covariance (ANCOVA), after optionally ranking transformation of the variable, with adjustment for sites and for other covariates suspected as affecting the outcome and which will be found different between the treatment groups.
- 5.6.5.3 Figures depicting the number of lesions by visit and by treatment group and depicting the reduction in number of lesions from Baseline to Day 56 will be generated
- 5.6.5.4 Binary variable will be defined based on the decrease in number of AK lesions at Day 56 according to a relevant cutoff (first quartile, median, third quartile or other cutoff computed by ROC curve sensitivity analysis). Comparative analysis of this variable will be applied between each of the active groups versus the placebo group using Chi-square test or Fisher's Exact test and using logistic regression with adjustment for site and for other covariates suspected as affecting the outcome and which will be found different between the treatment groups.

	DOCUMENT NUMBER: 029-BST-PLN-001	PAGE: 31 of 45
TITLE: Statistical Analysis Plan for study:  A Phase 2 Randomized, Double-Blind, Placebo-Controlled, Parallel-Cohort Study to Evaluate the Efficacy, Safety, Tolerability, and Pharmacokinetics of Once-Daily Application of Topical VDA-1102 Ointment for 28 Days in Subjects with Actinic Keratosis	EFFECTIVE DATE : 22/MAY/2017 REVISION NUMBER : 2.0	

5.6.5.5 If the two active VDA-1102 groups trend similarly then these two groups may be pooled and compared to the placebo group in order to achieve higher statistical power.

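### SAP 5.6.5.7 chooses the site groups from observed site differences, which distorts the site-adjusted efficacy models modestly: about 6% shrinkage, or type I error near 0.06 to 0.07, depending on an ANOVA the SAP does not specify

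*SAP*

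**What the plan says.** SAP 5.6.5.2 compares each active arm with placebo at Day 56 in two ways: by a "two-sample t-test, the non-parametric Wilcoxon-Mann-Whitney rank sum test for independent samples, or the Median test (as appropriate) and using the Analysis of Covariance (ANCOVA"), the ANCOVA being "with adjustment for sites and for other covariates suspected as affecting the outcome". The logistic model (5.6.5.4) and the mixed model (5.6.5.6) are adjusted for site too.

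SAP 5.6.5.7 then governs how site is coded. Its scope is stated as "For the ANCOVA analysis, logistic regression and mixed-effect model for repeated measures detailed above, if necessary". For these three model types the SAP provides that "grouping of sites will be done based on similarities and differences observed between sites by post-hoc contrasts of ANOVA". It gives no trigger for grouping, no number of groups, no contrast threshold, no minimum site size and no condition about blinding. It names neither the dependent variable of the ANOVA nor its other terms. Its place under the primary efficacy analysis implies the lesion decrease.

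The Protocol synopsis plans "Approximately 6 sites in the US and 3 in Israel". Protocol 12.1.1 and SAP 5.2.5 balance the arms "across all subjects enrolled (not per site) and within the PK Study Sub-Cohort". Protocol 17.2.1 has no site term and no site grouping; both come in with the SAP.

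**The concern.** With about 84 subjects over about 9 sites and no balance within site, the share of active subjects will vary between sites by chance. If the drug works, a site with more active subjects shows a larger mean decrease. Grouping sites by how their outcomes differ therefore sorts them partly by treatment mix, and adjusting for the groups can take out part of the effect being estimated.

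A grouping that was itself adjusted for treatment would avoid that, but it would fit the site term to the same data without charging for the search. In either case the covariate is chosen from the outcome under test, and the open wording leaves room to choose among several codings. At stake is how far the site-adjusted estimates and p-values can be taken at face value.

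**Working it through.** **Inputs from the documents.** About 9 sites (6 + 3, Protocol synopsis); 84 recruited, 75 evaluable, 25 per arm, effect size 0.83, two-sided alpha 0.045 (Protocol 17.1, SAP 5.3.2); 1:1:1 allocation, not balanced by site (Protocol 12.1.1, SAP 5.2.5).

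**Assumed, because the documents give no value.** Normal outcome with SD 1; between-site SD 0.3 (range 0 to 0.6); equal expected site sizes, with unequal sizes as a variant; sites merged by the smallest pairwise contrast, either until every remaining contrast has p < 0.05 or down to 2 or 3 groups.

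**Step 1: the plan's own figure.** Noncentrality 0.83 × √(25/2) = 2.93 on 48 df at two-sided 0.045 gives 80.7% power, against the stated 80%. Recruitment: 75/0.9 = 83.3, rounded up to 84. Both reproduce and are not in dispute.

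**Step 2: the mechanism.** The expected site mean is the site effect plus 0.83 × the active fraction. Take two sites of 9 subjects (84/9 ≈ 9.3), with 8 and 4 active subjects. Their means differ by 0.83 × (8/9 − 4/9) = 0.37 SD through treatment mix alone, more than the assumed between-site SD of 0.3.

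Under the null, groups built without treatment depend only on outcome and site, so they are independent of arm and the test keeps its level. Once treatment is in the ANOVA, the groups depend on arm and that protection is lost.

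**Step 3: simulation of one comparison** (6,000 trials per effect size, site SD 0.3; linear model of outcome on arm plus site term, tested at 0.045).

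| Site coding | Mean estimate, true 0.83 | Rejection rate, true 0 | Rejection rate, true 0.83 |
|---|---|---|---|
| No site term | 0.828 | 0.0448 | 0.7785 |
| Country (fixed in advance) | 0.828 | 0.0452 | 0.7738 |
| All 9 sites (fixed in advance) | 0.827 | 0.0435 | 0.7682 |
| Grouped, ANOVA without treatment: contrasts to p < 0.05 | 0.775 | 0.0435 | 0.7688 |
| same, 2 groups | 0.779 | 0.0440 | 0.7707 |
| same, 3 groups | 0.772 | 0.0435 | 0.7673 |
| Grouped, ANOVA with treatment: contrasts to p < 0.05 | 0.827 | 0.0623 | 0.8055 |
| same, 2 groups | 0.827 | 0.0622 | 0.8053 |
| same, 3 groups | 0.827 | 0.0617 | 0.8075 |

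Shrinkage without treatment in the ANOVA: (0.827 − 0.775)/0.827 = 6.3%, and 5.8% and 6.7% for 2 and 3 groups. Over site SD up to 0.6, unequal sites, and only one effective dose, the estimate stays at 0.77 to 0.79. Power is about that of the 9-site model.

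With treatment in the ANOVA the bias disappears and type I error is about 0.062. The Monte Carlo standard error is √(0.045 × 0.955/6000) = 0.0027, so the excess is not noise. Across settings and repeat runs the range is about 0.06 to 0.07.

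**Step 4: choice among p-values.** These runs assume site sizes 16, 13, 11, 9, 8, 6, 5, 4, 3 (total 75), 4,000 trials per setting, and grouping without treatment in the ANOVA.

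| Smallest p taken over | Site SD 0 | 0.3 | 0.5 |
|---|---|---|---|
| No site term, all sites | 6.2% | 6.6% | 6.8% |
| The same plus 2 and 3 groups | 6.9% | 7.7% | 8.2% |

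The groupings add about 0.7 to 1.3 points (the rounded rates at SD 0.5 differ by 1.4). A separate set of runs gave 5.4 to 6.6% for the first choice and 5.6 to 7.2% with groupings added, so end to end 0.2 and 0.6 points. The addition is therefore about 0.2 to 1.3 points.

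In the Step 3 runs, the smallest p over the 9-site model and all six groupings falls below 0.045 in 7.3% of null trials, or 8.0% with the no-site test added. That set includes the treatment-adjusted groupings, each already at about 6.2%. With a true effect of 0.83, the site codings disagree on significance in 9.3% of trials.

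**The case against.** The strongest reply is that little of consequence is touched. The sample size rests on a two-group t-test, the protocol's Day 56 comparison has no site term, and the unadjusted tests do not use the grouping. That stands. The table shells list one Day 56 ANCOVA (14.2-19) and one mixed model (14.2-20), both for the ITT population, not a menu of site codings. A shift of about 0.05 SD is small beside a standard error of √(2/25) = 0.28 SD, and no power is lost against a 9-site model. That stands too.

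A reader might infer that 5.6.5.7 by itself raises the false-positive rate to 7 or 8%. The documents do not support this. SAP 5.6.5.2 already plans both an unadjusted test and a site-adjusted ANCOVA without saying which decides, and that choice alone gives 5.4 to 6.8%. Dropping the site term is not an option that 5.6.5.7 creates.

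A reader might also infer that the effect is certainly biased towards zero, or that post-hoc means after unblinding. Neither follows. The SAP does not say whether treatment is in the ANOVA, and post-hoc contrast is the ordinary name for pairwise comparisons after an ANOVA. Grouping on blinded data would close the route to picking a p-value. It would not prevent the shrinkage, because contrasts without a treatment term need no treatment codes.

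Finally, grouping is conditional and may never happen. That limits how likely the harm is, but the SAP states no condition that would tell anyone when it applies.

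**Conclusion.** The concern holds in a limited form. If sites are grouped as 5.6.5.7 describes, the site-adjusted results are worse than with a site term fixed in advance under either reading of the ANOVA. Without treatment in it, the adjusted effect falls from 0.83 to about 0.77 to 0.79, with nominal type I error. With treatment in it, there is no shrinkage, but type I error is about 0.06 to 0.07 against 0.045. The extra false-positive risk from freedom over the grouping is small, and the stated increment applies to groupings made without treatment in the ANOVA.

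This does not invalidate the Day 56 comparison. It weakens the ANCOVA, the logistic models and the mixed model as support for it. The figures depend on the assumed site sizes, between-site SD and merging algorithm; the direction under each reading was the same in every setting tried.

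**What to change.** Replace SAP 5.6.5.7 with a pooling rule that uses no outcome data and is fixed before unblinding. For example, keep each site above a stated enrolment count (say, at least 6 subjects) as its own level and pool smaller sites within country. Use the same coding in the ANCOVA, logistic and mixed models, and delete the post-hoc ANOVA contrasts. The two fixed codings simulated, country alone and all 9 sites, gave estimates of 0.828 and 0.827 and type I error of 0.0452 and 0.0435.

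The cost is one paragraph, and a slight loss of precision if dissimilar small sites are pooled. The change does not settle the separate choice in 5.6.5.2 between unadjusted and adjusted tests; that needs one test named as primary.
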